### 8.1.3 Other study parameters

1. Patients' age and gender
2. Known history of pulmonary emphysema
3. Presence of pre-existent bullae on preoperative chest CT-scan
4. Thopaz data regarding the course of the amount of air leak and fluid production during postoperative drainage.
5. Performed surgical technique (e.g. chemical or mechanical pleurodesis)

## 8.2 Randomisation, blinding and treatment allocation

### 8.2.1 Randomisation

After informed consent, provided during the preoperative appointment with the lung surgeon at the outpatient clinic or during initial hospital admission, inclusion and exclusion criteria are entered into a computerised database (Research Manager). If the patient is eligible, an unchangeable computer generated number (anonymous) will be assigned to each patient and the patient will be randomised (1:1:1:1) for one of the four groups:

1. Chest tube duration at least 3 days plus TEA (current standard/usual care)
2. Chest tube duration at least 3 days plus single-shot PVB
3. Early chest tube removal plus TEA
4. Early chest tube removal plus single-shot PVB

Randomization will be done in variable block sizes of 4 and 8.

### 8.2.2 Stratification

1. Randomization will be stratified for type of hospital regarding chemical or mechanical pleurodesis. All participating hospitals use the same conditional technique for pleurodesis within their hospital, although between-hospital differences may exist, since some use chemical pleurodesis with talc and others perform mechanical pleurectomy (*see 'treatment of subject' paragraph*). As explained earlier, previous systematic reviews did not demonstrate evident differences among these techniques and firm recommendations are therefore still lacking (20–22). However, differences between these techniques may theoretically exist as a result of which we use this item as stratification factor.
2. Randomization will also be stratified by age  $\geq$  and  $<$  40 years, since age may influence the risk of recurrence or length of stay. Patients with PSP can grossly be subdivided into young (generally  $<$ 40 years) healthy persons with PSP based on smoking induced small apical bullae, and older patients ( $>$ 40 years) with bullae based on (unknown) pre-existing emphysema. The cut-off value of 40 years is frequently used in research on our topic.

### 8.2.3 Blinding

Blinding regarding early or late removal of the chest tube, or regarding the use of TEA or single-shot PVB is not possible.

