## **5. TREATMENT OF SUBJECTS**

### **5.1 General considerations**

#### *Surgery*

All included patients will undergo surgical pleurodesis through VATS, in order to achieve coalescence of the parietal and visceral pleura and prevent recurrence of pneumothorax. Pleurodesis can be achieved by either VATS pleurectomy or VATS chemical pleurodesis with talc.

With VATS pleurectomy the entire parietal pleura will be removed from approximately 2-3cm anterior to the spine (dorsally) to the mediastinal pleura anteriorly. The diaphragm will be left untreated, as well as the pleura covering the region of the subclavian vessels in the thoracic outlet.

With VATS talcage, the entire pleural space will be sprayed with sterilized talc, using a talc dispenser until all parietal pleura is covered with talc. Mediastinal, diaphragmatic and apical pleura may be treated with talc as well.

Thus far, both mechanical and chemical pleurodesis have been shown to be effective to provide pleurodesis. Several systematic reviews on this topic were not able to demonstrate solid preferences to one technique over the other, since available literature is of low quality and with high heterogeneity (20–22). As the chosen technique depends on the local preference or doctrine within hospitals, we are able by post-hoc subgroup analysis (non-randomized, but by hospital policy) to evaluate possible differences (hypothesis generating).

If during surgery ruptured bullae are visible (generally in the apex of the lung), they will be removed with wedge resection of the lung parenchyma. In case intact bullae are present in

the affected lung, wedge resection of these bullae is at the discretion of the lung surgeon. Performing a wedge resection is generally depending on the magnitude of the presence of bullae. Thus far it remains unclear whether bullectomy of intact bullae is an efficient procedure to prevent recurrent pneumothorax. Post hoc analysis of all CT images, as well as the existence of bullae during surgery, may provide further details on the question as to whether or not (and in what instances) remove intact bullae (hypothesis generating).

At the end of the operation, full expansion of the entire lung should be visualized and assured by the surgeon.

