#### *Intervention for pain management*

Before surgery, the skin of the incision site(s) will be injected with a local anaesthetic. At the beginning of surgery, before pleurectomy, a single shot PVB will be placed at 10 levels (T2-T11) by the surgeon with a local anaesthetic and 2-3mL per site under direct thoracoscopic vision. The injection site will be chosen at the paravertebral space, just lateral adjacent to the sympathetic trunk. This group will have no analgesic catheters for continued analgesia with local anaesthetics. No mobility restrictions are needed and no bladder catheter is given.

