### 11.2 Recruitment and consent

Consecutive patients with an indication for surgery for (recurrent) PSP are eligible for inclusion (see Figure 2). The decision for surgery is mostly made at the outpatient clinic, at the emergency room or during hospital admittance. When the indication is made and the patient is informed, the patient will also be informed about the trial by the (principal) investigator, the (supervising) doctor (thoracic or pulmonary department depending on local logistics) or (research) nurse and will receive the patient information folder (PIF). The time between informing the patient and surgery will differ varying between 0 to 2 weeks based on the current clinical condition and urgency. However, patients will be given enough time to read the PIF and to take a well-advised decision whether to participate or not. If the patient voluntarily agrees to participate, a written informed consent for inclusion will be obtained preferably by an independent research nurse or doctor, depending on local agreements. After informed consent is given, randomisation will take place (*see paragraph 8.2.1 randomisation*). Subsequently, the patient will have a meeting with the anaesthesiologist to discuss the anaesthesia and analgesia during the operation (either TEA or single-shot PVB based on randomisation).

Patients unable or refusing to provide informed consent will be treated according to current local clinical protocols.

Figure 2 Timeline overview of recruitment and consent

PIF = patient information form , IC = informed consent, POS = preoperative screening, POD = postoperative day

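### Section 8.2.3 is too broad: the chest tube arm is not needed until at least 4 hours after surgery, yet nothing withholds it from surgeon or patient before and during the operation

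*Protocol*

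**What the plan says.** **Allocation.** Section 8.2.1 places randomisation after consent, which it describes as follows: "After informed consent, provided during the preoperative appointment with the lung surgeon at the outpatient clinic or during initial hospital admission". Section 11.2 gives the same order ("After informed consent is given, randomisation will take place"), followed by the meeting with the anaesthesiologist and then surgery. It is a single draw: "the patient will be randomised (1:1:1:1) for one of the four groups". Each of the four groups is defined by a tube duration and an analgesic technique together.

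**Blinding.** Section 8.2.3 consists of one statement covering both factors: "Blinding regarding early or late removal of the chest tube, or regarding the use of TEA or single-shot PVB is not possible".

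**Who needs what, and when.** In section 5.3 the surgeon delivers the block: "a single shot PVB will be placed at 10 levels (T2-T11) by the surgeon". Section 8.2.4 says that the anaesthesiologist will know the analgesic arm and will discuss that technique with the patient. It does not say who learns the tube arm. Under section 5.3 the tube comes out no earlier than 4 hours after surgery in the early arms; under section 5.2 it comes out no earlier than POD 3 in the late arms.

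**What the surgeon decides.** In section 5.1, for intact bullae, "wedge resection of these bullae is at the discretion of the lung surgeon". For talc, all parietal pleura must be covered; beyond that, "Mediastinal, diaphragmatic and apical pleura may be treated with talc as well".

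**Withdrawal.** Section 8.4 lets patients leave at any time. Section 8.7 sends those who leave before the operation to local treatment and local follow-up. Section 8.6 rules out replacement.

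**The concern.** Section 8.2.3 treats the two factors alike, but they differ in when they must be known. The analgesic arm has to be known before the operation. The tube arm does not. As the protocol stands, nothing prevents the tube arm from being known during a period in which it serves no purpose and can do harm in two ways.

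First, a surgeon who knows that the tube may come out after 4 hours may resect or treat more (or less) than in a patient whose tube will stay until POD 3. The early-versus-late contrast would then mix tube timing with a different operation. This may affect recurrence, which is the safety outcome for this comparison and the item that the patient panel ranked first (8.1.1). Through air leak, which is a tube removal criterion, it may also affect tube duration and LOS. If surgeons were more thorough when early removal was planned, the bias would tend to hide harm from early removal; the opposite is also possible.

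Second, a patient who dislikes the assigned tube arm can withdraw before surgery and leave trial follow-up. Losses can then depend on the tube arm.

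**Working it through.** **1. Sequence of events against need for the tube arm**

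| Step | Source (Protocol) | Tube arm needed? | Analgesic arm needed? |
|---|---|---|---|
| Consent, then randomisation to a composite group | 8.2.1, 11.2 | No | No |
| Anaesthesia visit | 8.2.4, 11.2 | No | Yes |
| TEA placed, or PVB placed by the surgeon | 5.2, 5.3 | No | Yes |
| Wedge resection, pleurodesis | 5.1 | No | No |
| Tube placed and drainage threshold set | 8.2.4, 8.3 (not distinguished by arm) | No | No |
| 4 hours after surgery (early) or POD 3 (late), at the earliest | 5.3, 5.2 | **Yes** | already in use |

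The tube arm is first needed in the last row. Anyone who reads the composite group to learn the analgesic arm reads the tube arm too. This is an inference from 8.2.1, 5.3 and 8.2.3; no section says that surgeon or patient is told.

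**2. What stratification covers.** Section 8.2.2 stratifies by the hospital's pleurodesis type and by age. Neither balances a choice made in theatre after allocation.

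**3. The plan's own figures**

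- LOS sample size: difference 1.4 days, SD 4.5, two-sided alpha 0.05, power 80%. n = 2 × (1.960 + 0.842)² × (4.5/1.4)² gives 163 per group; the t-test version gives 163.1, so 164. Power at 164 is 80.4%. With 10% drop-out, 164/0.9 = 182.2, so 183 per group and 366 in total. The stated figures reproduce.
- Recurrence allowance: 9/164 = 5.49%, as stated.
- Expected recurrences per 164, from the review rates in section 5.3: late 0.0557 × 164 = 9.1; early 0.0459 × 164 = 7.5.

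**4. Scale of a shift in recurrence (assumed, not in the protocol).** A shift of 1 to 2 percentage points in one tube group is 0.01 × 164 = 1.6 to 0.02 × 164 = 3.3 cases. Divided by 9, that is 18% to 36% of the allowance.

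**5. Possible masking (assumed values).** Take the late risk as 5.57%. Let a share s of early-arm patients receive an extra resection with relative risk RR, so that early risk = (0.0557 + true excess) × (1 − s × (1 − RR)). The table gives the exact binomial probability that early minus late recurrences exceeds 9, with 164 per group, at a single look.

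| True excess | No extra resection | s = 10%, RR = 0.75 | s = 30%, RR = 0.50 |
|---|---|---|---|
| 5.49 points | 46% | 42% | 25% |
| 8 points | 75% | 72% | 52% |

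Example: (0.0557 + 0.08) × (1 − 0.30 × 0.50) = 0.1153, a mean difference of 164 × (0.1153 − 0.0557) = 9.8 cases and a probability of 52%.

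**6. Withdrawal.** The drop-out allowance is 366 − 328 = 38 patients, for any reason at any time. If losses were 5% in one tube group and 15% in the other (assumed), the gap would be 183 × 0.10 = 18 patients. LOS power would stay at about 80%, so the issue is bias, not power.

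**The case against.** Several stronger readings are tempting, and the documents do not support them.

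- *A reader might infer that the tube arm is disclosed to surgeon and patient before surgery.* The protocol never says so. The only pre-operative disclosure it describes is of the analgesic technique (8.2.4). Knowledge of the tube arm is a reasonable inference, no more.
- *A reader might infer that patients wait up to two weeks knowing their arm.* Section 11.2 says: "The time between informing the patient and surgery will differ varying between 0 to 2 weeks". Reading time, consent and randomisation all fall inside that interval. The wait after randomisation is not given; two weeks is only its upper bound.
- *A reader might infer that the extent of pleurodesis is left open.* It largely is not. Pleurectomy is total with stated borders, talc must cover all parietal pleura, and section 8.3 speaks of the entire pleural surface. Pleurodesis type follows hospital policy and is stratified. Ruptured bullae are always resected. What remains is intact bullae, a decision that section 5.1 ties generally to how extensive the bullae are, and three optional talc areas in talc hospitals.
- *A reader might infer that these choices are known to change recurrence.* Section 5.1 calls the benefit of resecting intact bullae unclear. Section 10.3 treats bullae on CT as a possible confounder for recurrence and LOS, which supports a possible effect and not an established one.
- *A reader might take the 38 patients as expected tube-driven withdrawals.* They are the whole drop-out allowance.

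It is also fair to say that 8.2.3 is right in its usual sense: once the tube is out or still in, patient and staff know. Later decisions on reintervention and readmission, which enter the recurrence definition, stay unblinded whatever is done before surgery. And a patient could still leave in knowledge of the TEA/PVB arm.

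All of this limits the size of the point. None of it gives a reason for the tube arm to be available before the operation is finished.

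**Conclusion.** The point holds in a limited form. Section 8.2.3 is too broad for the period before and during surgery: the tube arm could be concealed then, and no section does so. This leaves an avoidable route to performance bias, through wedge resection of intact bullae and optional talc areas, and to pre-operative withdrawal that depends on the tube arm.

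The conclusion rests on two things that the protocol leaves open: that the composite group is seen by surgeon and patient before the operation, and that the discretionary choices influence recurrence, air leak or LOS. Size and direction are unknown. The 1.6 to 3.3 cases, and the fall in the chance of exceeding the limit from 75% to between 52% and 72% at a true 8-point excess, show scale under assumed values and are not estimates. The sample size is unaffected. This is a cheap improvement to the design, not a defect that invalidates the comparison.

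**What to change.** Keep the single 1:1:1:1 randomisation and change only when its two parts are released.

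- **8.2.1 and 8.2.4:** Research Manager releases the TEA/PVB result before surgery. It releases the early/late tube result only after skin closure, once the operative CRF page (wedge resection, areas treated, lung expansion) has been entered.
- **8.2.3:** state that patient and surgical team are blind to the tube allocation until the end of surgery, and that blinding to the tube arm afterwards, and to the analgesic arm throughout, is not possible.
- **Consent text:** add a sentence saying that the tube arm is made known after the operation.

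The cost is a database setting, a protocol paragraph, and a post-operative release and hand-over step that has to work reliably in all 28 hospitals. No treatment rule, visit or sample size changes. The change does not blind post-operative decisions and does not prevent withdrawal in knowledge of the TEA/PVB arm.

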### 8.2.4 Treatment allocation

After randomisation, the patient will be scheduled for surgery with either a preoperatively placed TEA or intraoperatively placed single-shot PVB. When the patients present

themselves at the preoperative screening (POS) at the department of anaesthesiology, the anaesthesiologist will have knowledge of the analgesic technique to which the patient was allocated by randomisation. At this point, the anaesthesiologist will inform the patient about the technique that is going to be applicable at the time of the operation, as well as the risks and benefits of the technique (standard routine).

At the end of surgery, a chest tube, 16 – 20 French, will be left in place through one of the VATS incisions and connected to a Thopaz+ drainage system (Medela inc.). The Thopaz+ system will be set at -2cm H2O threshold (or -5cm H2O in case an old Thopaz system is used), guaranteeing a constant negative intrathoracic pressure of -2cm H2O (or -5cm H2O). Only above this level, the system will automatically apply suction until the intrathoracic pressure is assured to be below -2cm H2O (or -5cm H2O). Also, after randomisation the patients will undergo prompt chest tube removal 4 hours postoperatively when fulfilling the chest tube removal criteria or chest tube removal will be at POD3 when fulfilling the criteria.

### **8.3 Study procedures**

Preoperatively, during the process of informed consent, patients will be asked to complete a baseline QoR-15 questionnaire, QLQ-C30, EQ-5D health status, and baseline adjusted iMTA questionnaire. A preoperative CT-scan will be made to rule out possible secondary causes of pneumothorax in case a prior CT scan of the last 5 years is not available, which is standard of care.

The surgical procedures are described under paragraph 5 *'treatment of subjects'* and are part of standard general health care. In case of a pleurectomy, a total pleurectomy will be performed. In case of chemical pleurodesis, the entire pleural surface will be sprayed with talc. All procedures will be performed by VATS (either 1, 2 or 3 incisions). After surgery one postoperative chest tube will be placed mid-thoracic and a Thopaz system is used which is set at a threshold of -2cm H2O (or -5cm H2O). A chest X-ray will be performed ultimately 4 hours after surgery or in the morning of POD1 which is also part of routine postoperative care. In case all chest tube removal criteria are met (*see paragraph 5.2 'usual care' and 5.3 'interventions'*), the chest tube will be removed during expiration.

Regarding postoperative analgesia, the TEA catheter is placed preoperatively in awake patients and will be left in place for at least 2 days after surgery (*see paragraph 5.2 'usual care'*). Patients are allowed to mobilize under supervision when the motor function and sensibility are intact. The need for a urinary catheter will be in accordance with in house protocols of the participating hospital. In case of a single-shot PVB, patients will receive a single shot of 2-3 mL local analgesic in the paravertebral space per intercostal level from T2-

T11 (see paragraph 5.3 'interventions'), corresponding to a total volume of 20mL. The PVB will be placed perioperatively before performing pleurectomy. No urinary catheter or mobilisation restrictions are needed with single-shot PVB. Oral painkillers will include paracetamol, oxynorm and oxycontin. NSAIDs will not be allowed.

Postoperatively patients will be observed at the recovery room, and the first postoperative pain score will be noted. In case of hemodynamic stability and ultimately adequate pain control (NRS <4), they will afterwards be admitted to the ward. All patients will receive a diary in which pain scores (NRS 0-10; 0 = no pain, 10= worst imaginable pain) will be filled out 3 times daily (morning 2:00-12:00h, afternoon 12:01-18:00h, evening 18:01-1:59h) during 4 days. Also QoR-15 questionnaires and EQ-5D health status forms will be completed at daily basis during POD 0-3. In case patients will be discharged before POD 3, they will be asked to complete the diary at home and return it during the first postoperative outpatient clinic appointment.

After 4 weeks, patients will be seen at the outpatient clinic to check for complications and recurrence. In case of clinical signs of recurrence, such as chest pain and/or dyspnoea, a chest X-ray will be made to check for possible recurrent pneumothorax, which is part of routine postoperative care. During their visit, patients will provide a single pain score (NRS), QoR-15 questionnaire, QLQ-C30, EQ-5D health status and adjusted iMTA.

After 3 months and 1 year, patients will be contacted by telephone to check for possible recurrences (possibly diagnosed at other hospitals) or clinical signs of recurrence, as well as to assess the presence of thoracic pain with pain scores (NRS). They will also receive a EQ-5D-5L, QLQ-C30 and adjusted iMTA questionnaire to assess their health status and quality of life at these moments.

A detailed overview of all assessments is shown in the schedule of assessments (Table 1).

Table 1 Schedule of events

Assessment	Baseline/ Preoperative consultation	Day 0 surgery	POD* 1	POD 2	POD 3	POD 4	Outpatient clinic 4 weeks	3 and 12 months
Time point	t0	t1	t2	t3	t4	t5	t6	t7 and t8
Assessment of eligibility	X							
Written informed consent	X							
NRS pain score at rest	X						X	X
	Morning		X	X	X	X		
	Afternoon	X	X	X	X	X		
	Evening	X	X	X	X	X		
NRS pain score during movement	X						X	X
	Morning		X	X	X	X		
	Afternoon	X	X	X	X	X		
	Evening	X	X	X	X	X		
QoR-15 questionnaire	X	X	X	X	X		X	
EORTC QLQ-C30	X						X	X
Dosage use of opioids and analgesics		X	X	X	X	X	X	X
Patient satisfaction		X	X	X	X	X		
Recurrence PSP							X	X
Postoperative complications							X	
Patient mobility		X	X	X	X	X		
LOS**							X	
EQ-5D	X	X	X	X	X		X	X
iMTA – iMCQ and iPCQ	X						X	X

\*POD: postoperative day

\*\* LOS: length of hospital stay (including readmissions within 30 days after surgery)

#### **8.4 Withdrawal of individual subjects**

Subjects can leave the study at any time for any reason if they wish to do so without any consequence. In case subjects withdraw from the study after written informed consent, the reason will be asked and documented. In case no reason is given, this will be documented.

#### **8.5 Specific criteria for withdrawal**

1. In case of an allergic reaction to the investigated medicine
2. In case of secondary pneumothorax established during inclusion

#### **8.6 Replacement of individual subjects after withdrawal**

In our sample size calculation (*see paragraph 4.4*), we assumed a drop-out rate of 10%. Therefore, we will not replace individual subjects after withdrawal.

#### **8.7 Follow-up of subjects withdrawn from treatment**

In case subjects withdraw from participation before operation, these patients will undergo treatment and follow-up according to local treatment and follow-up protocols.

#### **8.8 Premature termination of the study**

The studied interventions in this study are already used (inter)nationally. According to a survey among Dutch thoracic surgeons early tube removal may be used in 31% and late tube removal in 69%; whereas regarding pain management TEA was used in 78% and locoregional techniques in 11% (9). Therefore, we expect the interventions do not lead to unexpected events.

We also expect recurrence rate to be equal in the early and late chest tube removal group, however since our patient panel emphasized the importance of recurrence rate, a data safety monitoring board (DSMB) will be installed regarding this outcome (*see paragraph 9.5 'Data safety monitoring board'*). When the incidence of recurrences after early chest tube removal exceeds the incidence after late tube removal by more than 9 cases, then early tube removal will no longer be applied and the study will continue with the two late tube removal subgroups, unless the DSMB advises otherwise.

